8.1.2. Summary Measure

Unless otherwise specified, endpoints / variables defined in Section 8.1.1 will be summarised using descriptive statistics, graphically presented (where appropriate) and listed.

Individual plasma GSK3335065 concentration-time profiles will be plotted by treatment (linear and semi-linear profiles). Blood sampling times will be related to the start of the infusion procedure. Actual sampling times will be used to calculate all the non-compartmental pharmacokinetic parameters. Individual concentrations of GSK3335065 in plasma will be listed and summarised by treatment and nominal time.

8.1.3. Population of Interest

The pharmacokinetic (PK) analyses will be based on the “PK Concentration” and “PK Parameter” population, unless otherwise specified.

8.1.4. Strategy for Intercurrent (Post-Randomization) Events

No statistical analysis will be completed for the pharmacokinetic endpoints, only summary statistics. Only the single dose data is available for analysis so this section is irrelevant to the PK analysis.

8.1.5. Statistical Analyses / Methods

Details of the planned displays are provided in [Appendix 10: List of Data Displays](#) and will be based on GSK IDSL Data Standards and statistical principles.

For each of the parameters mentioned above the following summary statistics will be calculated and tabulated by dose group for Part A:

- **Untransformed Data:** N, n, arithmetic mean, 95% confidence interval (CI) for the arithmetic mean, SD, median, minimum, maximum.
- **Loge-transformed Data:** Geometric mean, 95% CI for the geometric mean, SD of loge-transformed data and %CVb.

For tmax, tlast and t½ the summary statistics specified for untransformed data above will be generated.

9. PHARMACODYNAMIC BIOMARKER ANALYSES

9.1. Primary and Exploratory Pharmacodynamic Analyses

9.1.1. Endpoint / Variables

For KMO inhibition, the key endpoint of interest are the TRP metabolites (i.e. 3HK and KYN). As part of the exploratory analysis other metabolites such as TRP, KYNA, 3-HAT, XA, QA and other pathway components are of interest.

To investigate the metabolic pathway of GSK335065 in healthy participants, GSK335065-related material in plasma, urine and bile will be considered.

9.1.2. Summary Measure

Unless otherwise specified, endpoints / variables defined in Section 9.1.1 will be summarised using descriptive statistics, graphically presented (where appropriate) and listed by treatment group and planned relative time.

9.1.3. Population of Interest

The pharmacodynamic analyses and biomarker will be based on the “All Subjects” population, unless otherwise specified.

9.1.4. Strategy for Intercurrent (Post-Randomization) Events

No statistical analysis will be completed for the pharmacokinetic endpoints, only summary statistics. Only the single dose data is available for analysis so this section is irrelevant to the PD analysis.

9.1.5. Other details

Due a procedural issue in analysing cohort 3 pharmacodynamic samples, cohort 3 pharmacodynamic levels cannot be compared against cohort 1 and cohort 2.

For the pharmacodynamic related displays only: participants in cohort 3 (placebo or active) will be presented separately from cohorts 1 and 2 (i.e. placebo will not be pooled across cohorts). In cohorts 1 and 2, placebo PD samples were not collected.

Please note that the Anthranilic acid (AA) and quinolinic acid (QA) metabolites were not measured and as such they will not be reported.

11. APPENDICES

11.1. Appendix 1: Protocol Deviation Management and Definitions for Per Protocol Population

Inclusion Criteria

Number	Inclusion Description
1	Participant must be 18 to 50 years of age inclusive, at the time of signing the informed consent. In Part C (WONCBP) participants must be between 18 and 60 years of age.
2	Participants who are overtly healthy as determined by medical evaluation including medical history, physical examination, laboratory tests, and cardiac monitoring.
3	A subject with a clinical abnormality or laboratory parameter(s) which is/are not specifically listed in the inclusion or exclusion criteria, outside the reference range for the population being studied may be included only if the investigator in consultation with the Medical Monitor if required agree and document that the finding is unlikely to introduce additional risk factors and will not interfere with the study procedures.
4	Body weight >50kg and body mass index (BMI) within the range 18.5 – 32 kg/m ² (inclusive).
5	Abstinence/contraceptives: Length of time required for abstinence or use of contraceptives should take into account the reproductive toxicity profile including genotoxicity and teratogenicity, the size of the molecule, and the number of doses. Male participants: A male participant must agree to use contraception as detailed in Appendix 5 of the protocol during the treatment period and for at least 2 days after the last dose of study treatment and refrain from donating sperm during this period. Female participants: Only female participants of non childbearing potential (WONCBP) as defined in the protocol Appendix 5: Contraceptive Guidance and Collection of Pregnancy Information are eligible to participate.
6	Capable of giving signed informed consent as described in Appendix 3 which includes compliance with the requirements and restrictions listed in the informed consent form (ICF) and in this protocol.

Exclusion Criteria

Number	Inclusion Description
1	Alanine transaminase (ALT) and bilirubin >1.5xULN (isolated bilirubin >1.5xULN is acceptable if bilirubin is fractionated and direct bilirubin <35%).
2	Current or chronic history of liver disease, or known hepatic or biliary abnormalities (with the exception of Gilbert's syndrome or asymptomatic gallstones)
3	QTcF >450 msec from a mean of triplicate readings taken no more than 2 minutes apart
4	Clinically significant abnormal echocardiogram
5	The participant has a history or current evidence of depression, bipolar disorder, suicidal ideation and behaviour, or a lifetime history of suicide attempt.
6	cTn or BNP >ULN
7	Use of prohibited medication (Section 7.7 & Section 7.8) of protocol
8	The subject has participated in a clinical trial and has received an investigational product within the following time period prior to the first dosing day in the current study: 30 days, 5 half-lives or twice the duration of the biological effect of the investigational product (whichever is longer).
9	Exposure to more than four new chemical entities within 12 months prior to the first dosing day
10	Presence of hepatitis B surface antigen (HBsAg), positive hepatitis C antibody test result at screening or within 3 months prior to first dose of study treatment. For potent immunosuppressive agents, subjects with presence of hepatitis B core antibody (HBcAb) should also be excluded.
11	A positive pre-study drug/alcohol screen.
12	A positive test for human immunodeficiency virus (HIV) antibody.
13	Where participation in the study would result in donation of blood or blood products in excess of 500 mL within 84 days.
14	Poor or unsuitable venous access
15	History of regular alcohol consumption within 6 months of the study defined as: An average weekly intake of >14 units. One unit is equivalent to 8 g of alcohol: a half-pint

Number	Inclusion Description
16	History of sensitivity to any of the study medications, or components thereof or a history of drug or other allergy that, in the opinion of the investigator or Medical Monitor, contraindicates their participation.
17	History of smoking within 6 months of the study.

11.2. Appendix 2: Schedule of Activities

11.2.1. Protocol Defined Schedule of Events

Please refer to Protocol Amendment 3 Section 2 for full details of the Schedule of Activities.

11.3. Appendix 3: Assessment Windows**11.3.1. Definitions of Assessment Windows for Analyses**

Nominal time will be used for all analysis except PK analysis where planned and actual time will be used.

11.4. Appendix 4: Study Phases and Treatment Emergent Adverse Events

11.4.1. Study Phases

Assessments and events will be classified according to the time of occurrence relative to start and/or stop date and time of the study treatment

Study Phase	Definition
Pre-Treatment	Date \leq Study Treatment Start Date
On-Treatment	Study Treatment Start Date $<$ Date \leq Study Treatment Stop Date
Post-Treatment	Date $>$ Study Treatment Stop Date

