11.7.2.1. Handling of Missing and Partial Dates

Element	Reporting Detail
General	Partial dates will be displayed as captured in participant listing displays.
Adverse Events	
 • The eCRF allows for the possibility of partial dates (i.e., only month and year) to be recorded for AE start and end dates; that is, the day of the month may be missing. In such a case, the following conventions will be applied for calculating the time to onset and the duration of the event: 
 ○ Missing Start Day: First of the month will be used unless this is before the start date of study treatment; in this case the study treatment start date will be used and hence the event is considered On-treatment as per Appendix 4: Treatment States and Phases. ○ Missing Stop Day: Last day of the month will be used, unless this is after the stop date of study treatment; in this case the study treatment stop date will be used. • Completely missing start or end dates will remain missing, with no imputation applied. Consequently, time to onset and duration of such events will be

Element	Reporting Detail
	
missing.
 
 • AE time will be collected and if it is missing the following imputation will be applied: 
 ◦ If AE start time is missing then time is imputed as 00:00 unless the AE occurs on the first day of dosing in which case it has been imputed as the time of first dose. ◦ If AE end time is missing then time is imputed as 23:59. • Start or end dates which are completely missing (i.e. no year specified) will remain missing, with no imputation applied.

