11.7.2.2. Handling of Partial Dates

Element	Reporting Detail
Concomitant Medications	
 • Partial dates for any concomitant medications recorded in the CRF will be imputed using the following convention: 
 ◦ If the partial date is a start date, a '01' will be used for the day and 'Jan' will be used for the month ◦ If the partial date is a stop date, a '28/29/30/31' will be used for the day (dependent on the month and year) and 'Dec' will be used for the month. • The recorded partial date will be displayed in listings.
Adverse Events	
 • Any partial dates for adverse events will be raised to data management. If the full date cannot be ascertained, the following assumptions will be made: 
 ◦ If the partial date is a start date, a '01' will be used for the day and 'Jan' will be used for the month. ◦ However, if these results in a date prior to Week 1 Day 1 and the event could possibly have occurred during treatment from the partial information, then the Week 1 Day 1 date will be assumed to be the start date. ◦ The AE will then be considered to start on-treatment (worst case). ◦ If the partial date is a stop date, a '28/29/30/31' will be used for the day (dependent on the month and year) and 'Dec' will be used for the month. • The recorded partial date will be displayed in listings.

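### SAP 11.4.1 labels an adverse event at treatment start Pre-Treatment while 11.7.2.1 calls it on-treatment, and the 11.7.2.1 stop-day cap can end an event before it begins

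*SAP*

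**What the plan says.** Two sets of rules in the SAP govern when an AE is taken to occur.

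**Phase and flag (Appendix 4).** Section 11.4.1 opens: "Assessments and events will be classified according to the time of occurrence relative to start and/or stop date and time of the study treatment". Its table then assigns a date equal to or earlier than treatment start to Pre-Treatment, and makes On-Treatment strictly later than start, up to treatment stop. Section 11.4.2 defines the treatment-emergent flag with an inclusive lower limit: onset on or after treatment start. Its notes ask for clock times to be taken into account if they were collected.

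**Imputation (Appendix 7).** Section 11.7.2.1 covers AE dates with a missing day and says that "the following conventions will be applied for calculating the time to onset and the duration of the event". For a missing start day it uses the first of the month. If that falls before treatment, "the study treatment start date will be used and hence the event is considered On-treatment as per Appendix 4". A missing AE start time becomes midnight, "unless the AE occurs on the first day of dosing in which case it has been imputed as the time of first dose". For a missing stop day: "Last day of the month will be used, unless this is after the stop date of study treatment"; in that event the treatment stop date is substituted.

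Section 11.7.2.2 gives a second AE rule. It begins with a query step: "Any partial dates for adverse events will be raised to data management". If the full date still cannot be found, a start that would fall before Week 1 Day 1, but could have been during treatment, is moved to that day and counted as on-treatment. A partial stop date goes to a month end, with December supplied for the month and no cap at treatment stop.

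Under SAP 2.1, only Part A data are reported.

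**The concern.** An imputation rule that moves an event to the exact start of treatment is meant to be conservative: when in doubt, count the event as on drug. That works only if the phase definition includes the start, and 11.4.1 excludes it. Section 11.7.2.1 therefore cites Appendix 4 for a label that the phase table in that appendix does not give. The same AE could be Pre-Treatment by phase, on-treatment by the imputation text and treatment emergent by flag.

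The stop-day cap suits a long treatment period, where most events start and end on drug. After a single bolus, most of the observation time lies after treatment stop, so the cap acts on the events it fits least. Two programmers who followed the SAP faithfully could report different AE durations, one of them impossible. AEs are part of the primary endpoint, and a dataset this small is likely to be read event by event.

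**Working it through.** The plan gives no figure to reproduce. The check applies the rules literally.

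**Step 1: the boundary.** Let S be treatment start and X the AE onset.

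- 11.7.2.1, missing start day, first of month before S: X is set to S.
- 11.4.1: Pre-Treatment if X ≤ S. With X = S this is true. On-Treatment needs S < X, which is false. Label: Pre-Treatment.
- 11.7.2.1, own text: on-treatment.
- 11.4.2: S ≤ X is true, so the flag is treatment emergent.
- 11.7.2.2: on-treatment, if Week 1 Day 1 means the dosing day.

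Using clock times does not remove the tie. A missing AE time on the dosing day is set to the dose time, so X = S again and 11.4.1 again gives Pre-Treatment. The documents give no bolus duration. With assumed lengths of 0, 1, 5 and 30 minutes, an event at the dose time was Pre-Treatment under 11.4.1 and treatment emergent under 11.4.2 every time. One minute after the dose it was On-Treatment or Post-Treatment, never Pre-Treatment. By clock time, then, the conflict is confined to events at, or imputed to, the start.

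**Step 2: the stop-day cap.** Inputs:

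- Dosing date D.
- Treatment stop date. SAP 11.6.2 gives exposure = stop − start + 1 and calls the planned Part A treatment one day: 1 = stop − start + 1, so stop = start = D. This is an inference.
- Onset D + d, with d ≥ 1.
- L, the last day of the recorded stop month, which cannot be earlier than the onset month.

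Rule: stop = D if L > D, otherwise L. Since L ≥ D + d > D, the cap always applies, and

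stop − onset = D − (D + d) = −d days.

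The SAP does not say whether AE duration adds one day. If it does, the result is 1 − d, which is zero or below.

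**Step 3: how large d can be.** AEs are collected up to the follow-up visit (Protocol 9.2.1).

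- Cohorts 1 and 2 (Protocol Table 4): follow-up 7 to 14 days after the final dose, so d is at most about 14.
- Cohort 3 (Protocol Table 5): follow-up 7 to 14 days after Day 8 discharge, so at latest Day 8 + 14 = Day 22. With the dose on Day 1, d is at most 22 − 1 = 21. Dosing ended with the sentinels, which are two subjects under Protocol 5.1.1.

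Running the rule for every dosing date in a 365-day year and d = 1 to 21, with the stop in the onset month, gives 365 × 21 = 7,665 cases. All 7,665 have the stop before the onset.

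**Step 4: against 11.7.2.2.** Assumed dates: dose on 6 February, onset on 9 February, stop recorded only as February (28 days).

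| Rule | Imputed stop | Stop − onset |
|---|---|---|
| 11.7.2.1 | 6 February | 6 − 9 = −3 days |
| 11.7.2.2, recorded month kept | 28 February | 28 − 9 = +19 days |

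If 11.7.2.2 instead replaces the month with December, the stop is later still. The gap between the two sections therefore depends on the dates and on how 11.7.2.2 is read. On either reading 11.7.2.2 does not put the stop before the onset.

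**The case against.** The strongest reply is that nothing reported is shown to change. No display title in SAP Appendix 10 names study phase, treatment emergence, time to onset or AE duration. Partial dates are queried first, subjects were inpatients around dosing, and listings show the recorded partial date. If Cohorts 1 and 2 were full, about 8 + 8 + 2 = 18 subjects are involved. All of this stands and sets the size of the point. It does not make the rules consistent, and 11.7.2.1 says that its dates are used to calculate onset time and duration.

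On the boundary, Appendix 4 also contains 11.4.2, and on that reading 11.7.2.1 agrees with its own reference. That softens the contradiction but does not remove it, because the opening sentence of 11.4.1 covers events as well as assessments. It is also fair that the flag is a different variable from the phase, so a different label there is not in itself an error. Week 1 Day 1 is undefined, and Study Day in SAP 11.6.1 counts from randomisation. The firm conflict is between 11.4.1 and 11.7.2.1; the other two sections only support it.

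On the cap, the one-day statement in 11.6.2 is made for compliance, and Protocol 7.6 records a single date and time for a bolus. If no stop date is held, the cap has nothing to act on. The inference is plausible because the exposure formula needs a stop date, but it remains an inference. One could also read 11.7.2.2 as covering only dates with the month missing, since it supplies a month. Its opening words take in any partial AE date, so the overlap is real as written.

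Three stronger readings are tempting. A reader might infer that every dosing-day AE becomes Pre-Treatment and that On-Treatment is empty. That follows only if dates alone are compared, whereas 11.4.1 refers to date and time and 11.7.2.1 says AE time is collected. A reader might infer that AE counts or changes from baseline are distorted. AE tables use the All Subjects population and baseline is defined separately in SAP 5.2, so the documents do not show this. A reader might infer that the ventricular tachycardia that ended the study is misclassified. Nothing indicates that its date or time was incomplete.

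**Conclusion.** Both points hold as written, and both are minor. At equality with treatment start, 11.4.1 and 11.7.2.1 give opposite labels, by date or by clock time and for any bolus length. Under the missing-stop-day rule, stop minus onset is −d days for an AE that starts d days after a single dose. The rival rule in 11.7.2.2 gives a different answer, with no stated order between them.

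The second result assumes that the Part A treatment stop date is the dosing date. The support from 11.7.2.2 on the first point assumes that Week 1 Day 1 is the dosing day. The effect is limited to phase labels and to imputed AE timing and duration, for events whose full date or time cannot be recovered. Their number is not known and is probably small.

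**What to change.** In SAP 11.4.1, define Pre-Treatment as strictly before the dose date and time, and let On-Treatment include that moment. This brings it into line with 11.4.2 and 11.7.2.1, and with 11.7.2.2 once Week 1 Day 1 is understood as the dosing day.

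Replace the two AE rules in 11.7.2.1 and 11.7.2.2 with one, applied after the data-management query. It should retain any month that was recorded, drop the cap at treatment stop, and never place the stop before the onset.

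The cost is SAP wording and derivation code; no new data are needed.

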11.4.1.1. Study Phases for Concomitant Medication

Study Phase	Definition
Prior	If medication end date is not missing and is before enrolment
Concomitant	Any medication that is not a prior

NOTES:

- Please refer to [Appendix 7](#): Reporting Standards for Missing Data for handling of missing and partial dates for concomitant medication. Use the rules in this table if concomitant medication date is completely missing.

11.4.2. Treatment Emergent Flag for Adverse Events

Flag	Definition
Treatment Emergent	
 • If AE onset date is on or after treatment start date & on or before treatment stop date. (plus, washout or protocol-specified time limit (e.g. half-life of drug, certain number of days, etc.). • Study Treatment Start Date \leq AE Start Date \leq Study Treatment Stop Date [+ 5 x half-life].

NOTES:

- If the study treatment stop date is missing, then the AE will be considered to be On-Treatment.
- Time of study treatment dosing and start/stop time of AEs should be considered, if collected.

11.5. Appendix 5: Data Display Standards & Handling Conventions

11.5.1. Reporting Process

Reporting Process	
Software	

 The currently supported versions of SAS software 9.4 will be used. 	
Reporting Area	
HARP Server	UK1SALX00175
HARP Area	arenv/arprod/GSK3335065/mid201570/final_01
QC Spreadsheet	arenv/arprod/GSK3335065/mid201570/final_01/documents
Analysis Datasets	

 Analysis datasets will be created according to Legacy GSK A&R dataset standards 	
Generation of RTF Files	

 RTF files will be generated for the end of study SAC 	

11.5.2. Reporting Standards

Reporting Standards	
General	

 The current GSK Integrated Data Standards Library (IDSL) will be applied for reporting, unless otherwise stated: 
 4.03 to 4.23: General Principles 5.01 to 5.08: Principles Related to Data Listings 6.01 to 6.11: Principles Related to Summary Tables 7.01 to 7.13: Principles Related to Graphics 	
Formats	

 All data will be reported according to the actual treatment the participant received unless otherwise stated. GSK IDSL Statistical Principles (5.03 & 6.06.3) for decimal places (DP's) will be adopted for reporting of data based on the raw data collected. Numeric data will be reported at the precision collected on the eCRF. The reported precision from non eCRF sources will follow the IDSL statistical principles but may be adjusted to a clinically interpretable number of DP's. 	
Planned and Actual Time	

 Reporting for tables, figures and formal statistical analyses: 
 Planned time relative to dosing will be used in figures, summaries, statistical analyses and calculation of any derived parameters, unless otherwise stated. The impact of any major deviation from the planned assessment times and/or scheduled visit days on the analyses and interpretation of the results will be assessed as appropriate. Reporting for Data Listings: 
 Planned and actual time relative to study drug dosing will be shown in listings (Refer to IDSL Statistical Principle 5.05.1). Unscheduled or unplanned readings will be presented within the participant's listings. 	

Reporting Standards	

 Visits outside the protocol defined time-windows (i.e. recorded as protocol deviations) will be included in listings but omitted from figures, summaries and statistical analyses. 	
Unscheduled Visits	

 Unscheduled visits will not be included in summary tables. Unscheduled visits will not be included in figures. All unscheduled visits will be included in listings. 	
Descriptive Summary Statistics	
Continuous Data	Refer to IDSL Statistical Principle 6.06.1
Categorical Data	N, n, frequency, %
Reporting of Pharmacokinetic Concentration Data	
Descriptive Summary Statistics	Refer to IDSL Statistical Principle 6.06.1 Assign zero to NQ values (Refer to GUI_51487 for further details)
Reporting of Pharmacokinetic Parameters	
Descriptive Summary Statistics (Log Transformed)	N, n, geometric mean, 95% CI of geometric mean, standard deviation (SD) of logged data and [between and or within] geometric coefficient of variation (CV _{b/w} (%)) will be reported. [1] CV _b (%) = $\sqrt{(\exp(SD^2) - 1) * 100}$ (SD = SD of log transformed data) (MSE = mean square error from mixed effect model of loge-transformed data).
Parameters Not Being Log Transformed	T _{max} , t _{1/2} , t _{last}
Summary Tables	C _{max} , t _{max} , AUC(0-t), AUC (0-∞), CL, V, t _{1/2} , and t _{last} as data permit
Listings	All parameters collected in the dataset will be listed
Graphical Displays	

 Refer to IDSL Statistical Principals 7.01 to 7.13. 	

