2. SCHEDULE OF ACTIVITIES (SOA)

- The timing and number of planned study assessments, including safety, pharmacokinetic, pharmacodynamic/biomarker or other assessments may be altered during the course of the study based on newly available data (e.g., to obtain data closer to the time of peak plasma concentrations) to ensure appropriate monitoring.
- Any changes in the timing or addition of time points for any planned study assessments must be documented and approved by the relevant study team member and then archived in the sponsor and site study files, but will not constitute a protocol amendment. The Institutional Review Boards (IRB)/Independent Ethics Committees (IEC) will be informed of any safety issues that require alteration of the safety monitoring scheme or amendment of the Informed Consent Form (ICF).

2.1. Part A & C – Cohort 1, 2, 3, 4, 5, 6, 7, 8 & 13, single bolus dose, healthy volunteer subjects

Procedure	Screening (within 28 days of Day 1)	Study Period (Days)									Follow-up (7-14 days following discharge)	Notes
		-1	1	2	3	4	5	6	7	8		
Outpatient Visit	X										X	
Admission to Clinical Unit		X										
Inpatient Stay at Clinical Unit			←-----									
Discharge from Clinical Unit										X		Following completion of all assessments
Informed consent	X											
Inclusion and exclusion criteria	X	X										
Demography	X											
Full physical exam incl height and weight	X											
Brief Physical		X								X	X	Brief physical upon discharge from every cohort (Day 8)
Medical history (includes substance usage)	X											Substances: Drugs, Alcohol, tobacco and caffeine
Clinical Safety Laboratory Assessments (HIV, Hep B and Hep C Screen at screening only ¹)		X	X	X			X		X		X	Screening and day -1 safety labs must be in fasted state. ¹ If test otherwise performed within 3 months prior to first dose of study treatment, testing at screening is not required.
LFTs (ALT, AST, AP, direct and indirect Bilirubin)	X	X	X		X			X		X	X	

Procedure	Screening (within 28 days of Day 1)	Study Period (Days)									Follow-up (7-14 days following discharge)	Notes
		-1	1	2	3	4	5	6	7	8		
cTnI & BNP	X	X	X ²	X		X				X		² 6hrs post-dose
FSH	X											Females only, if required
Urine Drug/Alcohol Breath Test	X	X									X ³	³ Alcohol breath test only

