Treatment Period	For Cohorts 1 and 2, each subject will take part in four dosing session. During each study period subjects will be in-house from the day prior to dosing until Day 4 post dose when they will be discharged after post dose assessments have been completed. Subjects in Cohorts 1 and 2 will return to the unit approximately 3 weeks later to be dosed again on the following day. Following the completion of period 4, subjects will return as out-patients for any post-dose assessments.
Washout Period	Approximately 10 to 21 days between doses ^a .
Follow-up	7-14 days after final study drug administration in the Cohort. If warranted, additional follow-up visits may be scheduled.
Total Duration	Approximately 19 weeks

Table 5 Study Duration of Cohorts 3, 4, 5, 6, 7, 8 (Part A)

Screening	All screening assessments to be completed within 28 days prior to the first dose.
Treatment Period	Each subject will take part in one dosing session. During each study period subjects will be in-house from the day prior to dosing until Day 8 post dose when they will be discharged after post dose assessments have been completed. All subjects may return to the unit approximately 2 weeks after discharge from the unit as out-patients for any post-dose assessments.
Follow-up	Approximately 7-14 days after discharge from the unit. If warranted, additional follow-up visits may be scheduled.
Total Duration	Approximately 7 weeks

5.1.2. Part B: Multiple Ascending Dose (IV Bolus followed by an IV Infusion over 7 days) in Males

Prior to initiation of Part B, a review of all available safety, tolerability, PK and PD data from Part A will be conducted and potential changes to the dosing paradigm, safety observation period and assessments will be communicated in a future amendment to the protocol as appropriate.

Part B is a randomized, placebo-controlled, sequential panel, multiple ascending dose (IV bolus followed by continuous IV infusion over 7 days), double-blind (Sponsor unblinded) trial to evaluate the safety, tolerability, pharmacokinetics and pharmacodynamics of GSK3335065 in healthy male subjects. Subjects will be assigned to one of four Cohorts (9, 10, 11 or 12), and subjects will only participate in one single cohort. In each cohort subjects will be randomized to receive an IV bolus on day 1 subsequently followed by a continuous IV infusion for seven days. of either the active study drug (n=6) or placebo (n=2).

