11.7. Appendix 7: Reporting Standards for Missing Data

11.7.1. Premature Withdrawals

Element	Reporting Detail
General	
 • All participants who withdraw prematurely from the study/study drug will be documented and the reason for their withdrawal recorded in the final Clinical Pharmacology Study Report (CPSR). • Withdrawn participants may be replaced in the study except in Part A Cohorts (3-8). • All available data from participants who were withdrawn from the study will be listed and all available planned data will be included in summary tables and figures, unless otherwise specified.

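### SAP 11.5.2 drops out-of-window scheduled visits from every summary with no safety exception, and for Cohorts 1 and 2 the protocol gives two different follow-up windows

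*SAP*

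**What the plan says.** **The omission rule.** SAP 11.5.2 (Planned and Actual Time) says: "Visits outside the protocol defined time-windows (i.e. recorded as protocol deviations) will be included in listings but omitted from figures, summaries and statistical analyses". It does not separate safety from PK or PD data. The same section says of unscheduled visits: "Unscheduled visits will not be included in summary tables". Reclassifying a late visit as unscheduled would therefore not bring it back.

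**Other SAP text.** SAP 11.7.1, on withdrawn subjects, says that "all available planned data will be included in summary tables and figures, unless otherwise specified". SAP 11.3.1 sets no analysis windows and relies on nominal time. SAP 11.6.1 mentions a time window and a target day, but the SAP defines neither. SAP 11.2.1 sends the reader to Section 2 of Protocol Amendment 3 for the schedule.

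**The follow-up window for Part A.** Protocol Schedule of Activities 2.1 is headed "Part A & C – Cohort 1, 2, 3, 4, 5, 6, 7, 8 & 13, single bolus dose". Its last visit column reads "Follow-up (7-14 days following discharge", and its discharge column is Day 8. For Cohorts 1 and 2, Table 4 in Protocol 5.1.1 has subjects "in-house from the day prior to dosing until Day 4 post dose" and sets follow-up at "7-14 days after final study drug administration in the Cohort".

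**What is measured at follow-up.** Schedule 2.1 lists safety laboratory tests, liver function tests, 12-lead ECG and vital signs. Laboratory parameters, ECG and vital signs are primary endpoints (Protocol Section 4).

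**The concern.** In a by-visit summary at nominal time, a mistimed value blurs the mean for that time point, so omitting it can be defended. Worst-case, maximum and PCI tables ask something else: whether an abnormality was seen at any time after dosing. A follow-up ALT or QTc taken a few days late answers that as well as one taken on time, yet the rule removes both kinds of display alike.

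The omission is triggered by a window that the SAP does not define and that the protocol states in two ways for most of the subjects presumed dosed. The same visit can be in or out of the tables depending on which text is used to record the deviation.

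The study was stopped on a serious safety signal and its primary objective is safety. The follow-up visit is the one scheduled set of safety measurements after discharge in Schedule 2.1. If its values are lost, a table can show no post-discharge abnormality when one was measured.

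**Working it through.** **1. Do the inclusion clauses override the rule?** No. SAP 11.7.1 yields wherever something else is specified, and 11.5.2 specifies otherwise. 11.5.2 also asks for the impact of major timing deviations to be assessed, but that returns no value to a table.

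**2. Which displays lose data?** From SAP 11.10.5, the laboratory tables (2.9–2.17), hepatobiliary abnormalities (2.19), ECG (2.20–2.24) and vital signs (2.25–2.28). Adverse event tables are event-based and are not affected. Troponin and BNP have no follow-up entry in Schedule 2.1.

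**3. Do the listings catch what is dropped?**
- ECG: yes, all values and changes (Listings 28 and 29).
- Vital signs: yes, all values and changes (Listings 33 and 34).
- Numeric laboratory values: only in part. Listing 20 covers subjects with any PCI value, Listing 21 covers PCI values, and Listing 22 covers dipstick results.
- Example: the PCI threshold for ALT is 2×ULN or more (SAP 11.8.1). An out-of-window follow-up ALT above ULN but below 2×ULN, in a subject with no PCI value, leaves Table 2.11 and appears in no planned listing.

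**4. The plan's own duration, as a check on the anchor for Cohorts 3–8.** Table 5 states about 7 weeks.
- From discharge: 28 days screening + 7 days from dose to Day 8 + 14 = 49 days = 7.0 weeks (50 days, 7.1 weeks, if discharge is 8 days after dose).
- From dose: 28 + 14 = 42 days = 6.0 weeks.

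The discharge anchor reproduces the stated figure and agrees with Schedule 2.1.

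**5. The two windows for Cohorts 1 and 2, in study days (dose = Day 1).**
- Table 4, 7–14 days after dose: 1 + 7 to 1 + 14 = Days 8–15.
- Schedule 2.1 with Table 4's Day 4 discharge: 4 + 7 to 4 + 14 = Days 11–18 (Days 12–19 if Day 4 is counted as dose + 4).
- Schedule 2.1 with its own Day 8 discharge: 8 + 7 to 8 + 14 = Days 15–22.

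Table 4 and the Schedule overlap on Days 11–15 (or 12–15) with Day 4 discharge, and on Day 15 alone with Day 8 discharge. A visit on Days 8–10 is inside Table 4 and outside the Schedule on either discharge day. A visit on Days 16–18 is the reverse.

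**6. What one lost visit means.** The assumption is full Cohorts 1 and 2 plus the two Cohort 3 sentinels.
- Dosed: 8 + 8 + 2 = 18, of whom 16 are in Cohorts 1 and 2.
- 0.1 mg or 0.25 mg group: 1/6 = 16.7%.
- Pooled placebo: 1/(2 + 2 + 1) = 1/5 = 20%.
- 1.3 mg group: 1/1 = 100%.

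**7. How likely is any loss?** The documents give no count of out-of-window visits. If each of 18 subjects independently has probability q of a follow-up visit recorded as out of window, the chance of at least one omission is 1 − (1 − q)^18: 60% for q = 5%, 85% for q = 10%, 98% for q = 20%. These values of q are assumptions.

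**The case against.** **Omission needs a recorded deviation.** A visit one day late is not dropped automatically. Protocol Section 2 allows timing changes to be documented without an amendment, and SAP 4.1 has deviations reviewed before unblinding. This stands as a limit on how often the rule bites. It does not remove the rule, and Protocol Appendix 3 says that the sponsor's personnel remain unblinded throughout, so the review is a weaker safeguard than it sounds.

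**Much of the safety reading lies elsewhere.** Clinically significant abnormal results are adverse events (Protocol Appendix 4), ECG and vital signs are fully listed, no hypothesis is tested, and with about 18 subjects individual listings carry weight. This stands. The remaining loss is in the summary tables and in non-PCI numeric laboratory values.

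**The window for Cohorts 1 and 2 may lie in Amendment 2.** Table 4 describes the abandoned crossover, and SAP 2.3 refers to Amendment 2 for that design. It is therefore not shown that a contradictory window was applied to actual visits. But the SAP takes its schedule from Amendment 3 Section 2, whose heading includes these cohorts, so the plan as written leaves the question open.

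**Stronger readings that the documents do not support.**
- A reader might infer a conflict for Cohorts 3–8 as well, because Table 5 says "All subjects may return to the unit approximately 2 weeks after discharge from the unit as out-patients for any post-dose assessments". That sentence is permissive and sits in the treatment-period row. Table 5's own follow-up row agrees with Schedule 2.1.
- A reader might turn Days 16–18 into a rate, 3 of 8 days or 37.5%. That pairs Table 4's Day 4 discharge with a Schedule whose discharge column is Day 8, and it assumes visits spread evenly over the window.
- A reader might expect the loss to be greatest in subjects whose visits were displaced by an event or by the amendment. Nothing in the documents shows this.

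**Conclusion.** The concern holds in a bounded form. Followed as written, SAP 11.5.2 removes measured, scheduled, out-of-window safety results from tables whose purpose is to show whether an abnormality occurred, and no other clause restores them. For numeric laboratory values the listings do not fully make up for it.

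For Cohorts 1 and 2 the current protocol text gives two follow-up anchors that agree on 1 to 5 days, depending on the discharge day, so the exclusion is not reproducible from the documents. Those cohorts are 16 of the 18 presumed dosed, assuming they were filled and that only the sentinels were dosed in Cohort 3.

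One lost visit takes one-sixth of a 0.1 mg or 0.25 mg group or one-fifth of pooled placebo out of the follow-up summary. The number of visits affected is unknown, so this is a defect in the rule and not a demonstrated loss of data. Inpatient results taken on schedule and adverse event tables are untouched. It should be corrected, because the primary objective is safety and the change is small.

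**What to change.** In SAP 11.5.2:
- Keep the omission for PK and PD summaries by nominal time. Limiting it to PD alone would readmit mistimed PK samples to the concentration summaries.
- Include out-of-window scheduled safety assessments in all worst-case, maximum, PCI and hepatobiliary tables, and under their nominal visit in the by-visit safety tables.
- Footnote each such table with the number of assessments outside the window.

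State in the SAP which follow-up window is used to record deviations for Cohorts 1 and 2, and reconcile Table 4 with Schedule 2.1. Which window is clinically right is for the sponsor to settle. With those cohorts already discontinued, the statement serves deviation coding and reporting, not future visits.

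The cost is a few lines of SAP text and a change to one exclusion filter. The downside is that the follow-up row of the by-visit tables spans a somewhat wider range of days, which the footnote makes visible.
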